### **Examination Variables**

### **Explanation**

exam_id	Identifier: Anonymized imaging examination ID
patient_id	Identifier: Anonymized patient ID
exam_year	Year imaging examination was performed
pet_cat	Potential Confounder: PET Type - 1= "NM PET WHOLE BODY OUTSIDE WITH INTERPRETATION OR CONSULT"; 2="NM PET CT SKULL BASE TO MID THIGHS", "NM PET CT SKULL BASE TO MID THIGH WITH DEDICATED BRAIN", "NM PET CT SCALP TO TOES"; 3="NM PET CT NEUROENDOCRINE TUMOR LOCALIZATION"; 4 = "NM PET CT PROSTATE CANCER IMAGING"; 5= "NM PET CT BONE SCAN SODIUM FLUORIDE"
exam_care_level	Potential Confounder: care level at time of examination - E = Emergency; I = Inpatient; O = Outpatient
ReferringProviderDepartment	Potential Confounder: specialty of provider who ordering imaging examination; specialties categorized into 6 broader groups: surgery, pediatrics, emergency medicine, neurology, oncology, other medicine, and missing
exam_site	Potential Random Effect: anonymized location of scanner where examination performed

#### **Additional Patient Variables**

#### **Explanation**

sex	Demographic: 1 = male; 2 = female; 3 = other/unknown
adi	Demographic: national area deprivation index on scale 0 (low deprivation) to 100 (high deprivation) based on listed home address in 2025
language	Demographic: self-reported language
race	Demographic: self-reported race
ethnicity	Demographic: self-reported ethnicity
smoking	Potential Confounder: 0 = never; 1 = former; 2 = active; No_self-report = not reported; most recently recorded prior to imaging
alcohol	Potential Confounder: 0 = never; 1 = occasional; 2 = heavy; most recently recorded prior to imaging
obesity	Potential Confounder: 1 = diagnosis of obesity (ICD-10 E66, ICD-9 278.00 or 278.01) at time of imaging examination OR OR cacluated BMI >30 at timepoint within 1 year before and closest to imaging examination; 0 = no diagnosis of obesity or BMI >30
metabolic_syndrome	Potential Confounder: 1 = diagnosis of metabolic syndrome (ICD-10 , ICD-9 277.7) at time of imaging examination; 0 = no diagnosis of metabolic syndrome at time of imaging examination
mi	Mortality Risk Adjustor: Myocardial Infarction: ICD-10 I21.9; ICD-9 410; recorded prior to date of imaging examination
chf	Mortality Risk Adjustor: Congestive Heart Failure: ICD-10 I50; ICD-9 428; recorded prior to date of imaging examination
pvd	Mortality Risk Adjustor: Peripheral Vascular Disease: ICD-10 I70, I73; ICD-9 443, 440.2, 440.3, 440.4; recorded prior to date of imaging examination

cva	Mortality Risk Adjustor: Cerebrovascular Accident: ICD-10 I60-I63, G45; ICD-9 430-438; recorded prior to date of imaging examination
dementia	Mortality Risk Adjustor: Dementia: ICD-10 F01-F03; ICD-9 290; recorded prior to date of imaging examination
cpd	Mortality Risk Adjustor: Chronic Pulmonary Disease: ICD-10 J42-J44; ICD-9 491-492; recorded prior to date of imaging examination
ctd	Mortality Risk Adjustor: Connective Tissue Disease: ICD-10 M30-M36; ICD-9 710; recorded prior to date of imaging examination
pu	Mortality Risk Adjustor: Peptic Ulcer Disease: ICD-10 K25-K28; ICD-9 531-534; recorded prior to date of imaging examination
ld	Mortality Risk Adjustor: Liver Disease: ICD-10 K70-K77; ICD-9 570-573; recorded prior to date of imaging examination
dm	Mortality Risk Adjustor: Diabetes Mellitus: ICD-10 E8-E13; ICD-9 249-250; recorded prior to date of imaging examination
hemiplegia	Mortality Risk Adjustor: Hemiplegia: ICD-10 G81; ICD-9 342; recorded prior to date of imaging examination
ckd	Mortality Risk Adjustor: Chronic Kidney Disease: ICD-10 N18; ICD-9 585; recorded prior to date of imaging examination
cancer	Mortality Risk Adjustor: Cancer: ICD-10 C00-C96; ICD-9 140-209; recorded prior to date of imaging examination
obesity_icd	Mortality Risk Adjustor: Diagnosis of obesity (ICD-10 E66, ICD-9 278.00 or 278.01) at time of imaging examination
bmi	Mortality Risk Adjustor: Body mass index at time of imaging examination
hncancer_binary	Mortality Risk Adjustor: Head/Neck Cancer: ICD-10 C00-C14; ICD-9 140-149; recorded prior to date of imaging examination
radiation_binary	Mortality Risk Adjustor: Radiation Therapy: CPT 77401-77416, G6003-G6014, 77385-77386, G6015-G6016
priorneckradiation	Mortality Risk Adjustor: Prior head/neck cancer radiation therapy (ICD-10 C00-C14 or ICD-9 140-149 and CPT 77401-77416, G6003-G6014, 77385-77386, or G6015-G6016 both recorded prior to date of imaging examination, then priorneck radiation =1; otherwise, 0)
Fiveyr_atPET	Mortality Risk Adjustor: 5 year survival probability associated with cancer dx received before PET exam (if multiple cancers before PET, lowest survival probability)
NeckNodes	Potential Confounder: 1= PET-CT report indicates that there are neck or supraclavicular lymph node metastases
AxillaryNodes	Potential Confounder: 1= PET-CT report indicates that there are axillary lymph node metastases
MediastinalNodes	Potential Confounder: 1= PET-CT report indicates that there are mediastinal (including paratracheal, paraesophageal, prevascular, subcarinal, perihilar, or hilar) lymph node metastases
AbdominalNodes	Potential Confounder: 1= PET-CT report indicates that there are abdominal (including peri-portal, celiac, mesenteric, retroperitoneal, iliac) lymph node metastases
InguinalNodes	Potential Confounder: 1= PET-CT report indicates that there are inguinal lymph node metastases

Brain	Potential Confounder: 1= PET-CT report indicate that there is likely primary malignancy or metastases in the lungs
Face	Potential Confounder: 1= PET-CT report indicate that there is likely primary malignancy or metastases in the face (e.g. pharynx, salivary glands, etc)
Lung	Potential Confounder: 1= PET-CT report indicate that there is likely primary malignancy or metastases in the lungs
Pleura	Potential Confounder: 1= PET-CT report indicate that there is likely primary malignancy or metastases in the pleura
Mediastinum	Potential Confounder: 1= PET-CT report indicate that there is likely primary malignancy or non-nodal metastases in the mediastinum
Liver	Potential Confounder: 1= PET-CT report indicate that there is likely primary malignancy or metastases in the liver
Spleen	Potential Confounder: 1= PET-CT report indicate that there is likely primary malignancy or metastases in the spleen
Kidney	Potential Confounder: 1= PET-CT report indicate that there is likely primary malignancy or metastases in the kidneys
Adrenal	Potential Confounder: 1= PET-CT report indicate that there is likely primary malignancy or metastases in the adrenal glands
Pancreas	Potential Confounder: 1= PET-CT report indicate that there is likely primary malignancy or metastases in the pancreas
GI	Potential Confounder: 1= PET-CT report indicate that there is likely primary malignancy or metastases in the GI tract
Pelvis	Potential Confounder: 1= PET-CT report indicate that there is likely primary malignancy or non-nodal metastases in the pelvis
Peritoneum	Potential Confounder: 1= PET-CT report indicate that there is likely primary malignancy or metastases in the peritoneum/omentum
Bone	Potential Confounder: 1= PET-CT report indicates that there is likely primary malignance or metastases in the bones
Muscle	Potential Confounder: 1= PET-CT report indicate that there is likely primary malignancy or metastases in the muscles

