## 4 STUDY DESIGN

### 4.1 OVERALL DESIGN

We hypothesize that all-cause mortality in patients with an incidental thyroid nodule on PET-CT who did not have thyroid ultrasound (the exposure) within 3 months of the PET-CT is non-inferior within a 5% margin to those who have thyroid ultrasound at 7-years. That is, among patients with an incidental thyroid nodule on PET-CT, mortality is no more than 5% larger (in absolute difference) for those who do not have thyroid ultrasound compared to those who do. We will also report mortality differences at landmark timeframes of 1-year, 3-years, 5-years, and 10-years.

Understanding an expected 30%-50% baseline 10-year mortality rate in patients who undergo PET imaging at our institution, a 5% non-inferiority margin was chosen based on the most conservative proposed margin by 2 thyroid endocrinologists (one did not respond) and a head and neck surgeon (other proposed margins were 7% and 10%). This margin decision was informed by typical margins of 5% to 10% used in non-inferiority trials of medications with outcomes involving mortality and by recent non-inferiority trials of thyroid cancer treatments. The observational nature of this non-inferiority study and absence of prior studies that show effect sizes for the reference make ideal margin point-estimate and fixed-estimate calculations impossible, but our expert panel method is supported as a practical necessity to provide guidance on the fraction of the point estimate of the active comparator that stakeholders are willing to lose at a cost of gaining other advantages (in this case, likely fewer biopsies and surgeries), as in the point-estimate margin calculation method. Given this careful pre-specification of our margin with this panel decision, we will follow published methodology recommendations and consider re-evaluation of the margin based on the secondary benefits seen in the emulated trial or we may conduct the final analysis without reference to a margin. These decisions will be clearly detailed in final manuscripts.

To estimate group differences in mortality, we will conduct a non-inferiority emulated target trial utilizing clone-censor weighting to address potential immortal time bias introduced by the 3-month grace period. We will adjust for all variables labeled as demographic, potential confounder, or mortality risk adjustor in as listed in the Section 7, below.

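### The ICD-9 and ICD-10 halves of several comorbidity adjustors do not match, most clearly for MI (all of 410 against only I21.9), so avoidable misclassification enters the adherence weights

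*Combined protocol and SAP*

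**What the plan says.** The table of additional patient variables in Section 7 defines each comorbidity by an ICD-10 list and an ICD-9 list:

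- **MI:** "Mortality Risk Adjustor: Myocardial Infarction: ICD-10 I21.9; ICD-9 410; recorded prior to date of imaging examination".
- **Diabetes:** "Mortality Risk Adjustor: Diabetes Mellitus: ICD-10 E8-E13; ICD-9 249-250; recorded prior to date of imaging examination".
- **Cerebrovascular accident (CVA):** "Mortality Risk Adjustor: Cerebrovascular Accident: ICD-10 I60-I63, G45; ICD-9 430-438; recorded prior to date of imaging examination".
- **Peripheral vascular disease (PVD):** "Mortality Risk Adjustor: Peripheral Vascular Disease: ICD-10 I70, I73; ICD-9 443, 440.2, 440.3, 440.4; recorded prior to date of imaging examination".
- **Connective tissue disease (CTD):** M30-M36 in ICD-10 and 710 in ICD-9.
- **Heart failure, for comparison:** "Mortality Risk Adjustor: Congestive Heart Failure: ICD-10 I50; ICD-9 428; recorded prior to date of imaging examination", a whole category on both sides.

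Section 4.1 fixes the adjustment set: "We will adjust for all variables labeled as demographic, potential confounder, or mortality risk adjustor". In the examination variables of Section 7, exam_year is collected but carries none of those three labels. Section 1.2 (steps 3 and 4) puts the baseline factors into the adherence model. The outcome model contains only time, treatment and their interaction. Section 7 says that the variables are pulled by SQL and Python scripts. It gives no rule for exact, prefix or range matching of codes, and no look-back limit for these comorbidities.

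**The concern.** A flag built from two code lists should mean the same thing whichever list a patient's history was recorded in. Here it does not. A patient whose MI was coded in ICD-9 is flagged for anything in category 410. A patient whose MI was coded in ICD-10 is flagged only for I21.9. As histories move from one system to the other, the same variable measures different things in early and late PET years.

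This matters because the adherence weights carry all of the baseline adjustment. A missed comorbidity that predicts both ultrasound use and death leaves residual confounding in the risk difference that is compared with the 5-point margin. Exam year is not in the stated adjustment set, so a drift in capture would not be absorbed there. The plan has no code-mapping check and no table of comorbidity by year that would reveal it.

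**Working it through.** The documents give no figure for comorbidity prevalence, code sensitivity or residual bias, so there is no planned number to reproduce. The check has three parts.

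**1. The code lists side by side**

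| Adjustor | ICD-10 | ICD-9 | Reading |
|---|---|---|---|
| MI | I21.9 | 410 | ICD-10 clearly narrower |
| CVA | I60-I63, G45 | 430-438 | ICD-10 looks narrower |
| PVD | I70, I73 | 443, 440.2-440.4 | ICD-10 looks wider |
| CTD | M30-M36 | 710 | ICD-10 looks wider |
| Diabetes | E8-E13 | 249-250 | lower bound malformed |

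I21.9 is the only decimal ICD-10 subcode among the comorbidity definitions. All the others are whole categories or ranges. The MI mismatch is therefore visible from the plan's own notation. The readings for CVA, PVD and CTD rest on the printed width of the lists.

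Diabetes depends on how the script reads the range:
- As a literal string range it is empty, because E8 sorts after E13.
- As a prefix, E8 adds E80-E89.
- Read as E08-E13, it is the natural partner of 249-250.

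**2. Drift with PET year**

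The documents give no changeover date. They are consistent with one near the start of accrual: histories before the PET use both systems, while the thyroid cancer outcome after the PET uses ICD-10 only. Assume 1 October 2015. The mean share of look-back time that falls in ICD-10 is then:
- 5-year look-back, PET years 2015 to 2021: 0.006, 0.150, 0.350, 0.550, 0.750, 0.944, 1.000. With even accrual the mean is 3.75 / 7 = 0.54.
- 10-year look-back: from 0.003 in 2015 to 0.575 in 2021, with a mean of about 0.28.

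With no look-back limit, later patients keep their ICD-9 history, so the longer window is closer to the rule as written.

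**3. Size through MI**

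*Simple form.* Bias = prevalence gap between arms x mortality difference. Assuming a gap of 3 to 5 points, 20 points of added mortality, and MI wholly uncaptured:
- 0.03 x 0.20 = 0.6 points, and 0.05 x 0.20 = 1.0 point.
- Diluted by the mean ICD-10 share, with no ICD-10 MI captured at all: about 0.3 to 0.5 points (x 0.54) or 0.2 to 0.3 points (x 0.28).

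*Standardised form.* Let M be the captured MI flag, with specificity 1, sensitivity s and no true ultrasound effect. Then bias = P(M=0) x [risk(no US, M=0) - risk(US, M=0)]. Assumed inputs: MI prevalence 5-15%; mortality 10 or 20 points higher with MI; ultrasound uptake with MI v without of 10% v 15%, 10% v 20%, or 20% v 40%. The baseline risk cancels.

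Worked case: prevalence 10%, s = 0.5, uptake 10% v 20%, 20 points of added mortality.
- P(M=0) = 1 - 0.05 = 0.95. MI share within M=0 = 0.05 / 0.95 = 0.0526.
- MI share without ultrasound = 0.0526 x 0.9 / (0.0526 x 0.9 + 0.9474 x 0.8) = 0.0588.
- MI share with ultrasound = 0.0526 x 0.1 / (0.0526 x 0.1 + 0.9474 x 0.2) = 0.0270.
- Bias = 0.95 x (0.0588 - 0.0270) x 0.20 = 0.0060, or 0.60 points.

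| Sensitivity across the whole cohort | Bias, points |
|---|---|
| 1 | 0.00 |
| 0.8 | 0.04 to 0.49 |
| 0.5 | 0.10 to 1.17 |
| 0.2 | 0.15 to 1.79 |
| 0 | 0.19 to 2.19 |

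If every ICD-10 MI were missed and MI records were spread evenly over the look-back, average sensitivity would be about 1 - 0.54 = 0.46 or 1 - 0.28 = 0.72. The rows for 0.5 and 0.8 are therefore the relevant ones. In the 0.5 row, 17 of the 18 scenarios lie below 1 point.

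**The case against.** A reader might infer that the weights systematically under-adjust later patients. The documents do not support that. MI and CVA look narrower in ICD-10, but PVD and CTD look wider, so there is no common direction.

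Nor do they support near-complete capture in 2015 and poor capture later. The changeover date is an assumption, and earlier ICD-9 history is retained. The ICD-10 share of look-back time is also not a sensitivity: the documents do not show how many ICD-10 MI records carry I21.9.

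Diabetes is most likely a dropped zero. A script written from the intended range would work, and the prefix reading over-captures rather than misses. This stands as a reason not to claim lost diabetes cases. It does not make the printed range usable, because no matching rule says how it will be run.

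Metabolic syndrome appears as "diagnosis of metabolic syndrome (ICD-10 , ICD-9 277.7) at time of imaging examination". The blank may be text lost in reading the PDF, so it is not counted as a defect.

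On size, many correlated adjustors (age, heart failure, PVD, kidney disease, smoking, BMI) would absorb part of any missed MI. Bias also needs missed MI to predict ultrasound use, for which the documents give no evidence. If patients with MI get fewer ultrasounds, the bias raises the apparent risk without ultrasound and works against concluding non-inferiority. If they get more, it runs the other way. All of this stands, and it limits the point to a correctable definition error. The MI mismatch itself is unaffected.

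**Conclusion.** The MI definition is wrong as written, the diabetes range cannot be run reliably as printed, and the CVA, PVD and CTD pairs need checking for scope. The consequence is avoidable misclassification in the adherence weights, drifting gradually with PET year if the changeover fell near the start of accrual.

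Through MI, the effect is probably well under 1 point of the 5-point margin. That rests on assumed prevalence, uptake, excess mortality, changeover date and even accrual. The sign is unknown. This should be corrected before the analysis dataset is built. It is not a demonstrated threat to the 7-year conclusion.

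**What to change.** In the Section 7 variable table:

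1. Define MI at category level in ICD-10 (all of I21, with I22) to match 410.
2. Correct the diabetes range to E08-E13.
3. Bring the CVA, PVD and CTD pairs to the same scope in both systems.
4. State the code-matching rule (exact, prefix or range), and say whether all available history is searched.
5. Confirm that the source document holds an ICD-10 code for metabolic syndrome.

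Before analysis, tabulate the prevalence of every code-based adjustor by exam_year and look into any step. Give exam_year an adjustment label so that it enters the adherence model. Adding it does not recover MIs missed within a year, so the code lists come first.

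The cost is code-list edits, one table and one extra covariate, with no new data. Version 1.1 already revised covariates in this section.

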	
Kaplan-Meier to estimate probability of mortality in each arm
 
Construct a 95% confidence interval for the absolute difference between the two arms, <math>\Delta_{RD}</math>
 
Taking the type I error rate, alpha, to be 0.05, non-inferiority is concluded if the upper limit of a two-sided 90% = 100(1-2alpha)% confidence interval for <math>\Delta_{RD}</math> is less than the prespecified margin.
	
baseline; one clone assigned to each treatment strategy.
 
2. Person-time for each clones is censored when their observed treatment strategy is non-adherent. That is, clones assigned to undergo thyroid ultrasound within 3 months are censored at 3 months of follow-up if no ultrasound is performed. Similarly, clones assigned to not undergo an ultrasound within 3 months are censored at the time an ultrasound is performed.
 
3. A pooled logistic regression model is fit for the (conditional) probability of adherence, adjusting for a priori specified baseline factors that predict adherence.
 
4. A marginal structural pooled logistic regression model is fit to the mortality outcome data, as a function of time and treatment (with interaction), using inverse-probability of censoring weights from step 3.
 
5. Treatment-specific marginal probabilities of all-cause mortality are estimated from the fit in step 4, from which the causal risk difference, <math>\Delta_{RD}</math>, is estimated along with a two-sided 90% = 100(1-2alpha)% confidence interval (constructed via the bootstrap).
 
6. Taking the type I error rate, alpha, to be 0.05, non-inferiority is concluded if the upper limit of a two-sided 90% = 100(1-2alpha)% confidence interval for <math>\Delta_{RD}</math> is less than the prespecified margin.

Secondary Outcomes	
Cumulative over 7-years from PET:
 
Number of thyroid cancers
 
Number of thyroid ultrasounds
	
Cumulative incidence rate over 7-years from PET or to the end of the study period

	Number of thyroid biopsies Number of thyroid surgeries	
Exploratory Analysis	Types of thyroid cancer diagnoses	Same

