We will stratify analyses based on baseline disease severity (estimated 5-year relative survival risk) and disease status (progression, lymph node involvement, other sites of metastases).

All subjects will be accrued from the Mass General Brigham healthcare system, which includes two academic medical centers, a specialty head and neck hospital, and multiple community hospitals and numerous community clinics.

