#### 8.4.5 SUB-GROUP ANALYSES

Stratified analyses will be performed based on baseline 5-year relative survival probabilities, calculated on the basis of the known cancer diagnoses, and disease status at the time of PET.

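### Fiveyr_atPET gives recent and remote diagnoses of the same cancer one score, and no Section 7 covariate records time since diagnosis, so some residual confounding is possible

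*Combined protocol and SAP*

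**What the plan says.** - **Definition.** Section 7 (Additional Patient Variables) describes `Fiveyr_atPET`, labelled a mortality risk adjustor, as "5 year survival probability associated with cancer dx received before PET exam (if multiple cancers before PET, lowest survival probability". It does not name the survival source, say whether stage is used, or set a look-back window.
- **Cancer history.** The general cancer indicator is also open-ended: "Cancer: ICD-10 C00-C96; ICD-9 140-209; recorded prior to date of imaging examination".
- **Use in adjustment.** Section 4.1 states "We will adjust for all variables labeled as demographic, potential confounder, or mortality risk adjustor", so the score belongs to the adjustment set. Step 3 of the emulated analysis in Section 1.2 fits the adherence model "adjusting for a priori specified baseline factors that predict adherence".
- **Use in stratification.** Section 4.1: "We will stratify analyses based on baseline disease severity (estimated 5-year relative survival risk) and disease status". Section 8.4.5: "Stratified analyses will be performed based on baseline 5-year relative survival probabilities, calculated on the basis of the known cancer diagnoses", followed by "disease status at the time of PET".
- **Current disease.** Section 7 also lists 5 nodal and 15 organ or site flags read from the index PET report, all labelled potential confounders.
- **Population.** Section 5.1 places no restriction on the indication for the index PET-CT, so staging, surveillance and remote-history patients can all enter.

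**The concern.** Five-year survival by diagnosis runs from the date of diagnosis. The variable's name and the Section 4.1 label of baseline severity imply prognosis at the PET. The two agree only for a new diagnosis, or for a cancer whose hazard does not change with time. Keeping the lowest value among all past cancers also lets an old poor-prognosis cancer override a newer, milder one.

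Prognosis plausibly influences both death and the decision to work up a thyroid nodule. If patients with equal scores differ in real prognosis, and that difference is related to having an ultrasound, the weights leave part of it unadjusted. Separately, the low-survival stratum may pool patients with very different outlooks, which makes its estimate hard to interpret.

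**Working it through.** **1. The plan's own figures.** `Fiveyr_atPET` enters no stated number. The power simulation in Section 8.2 used age and sex only, so there is nothing to reproduce. The benchmark for size is the 5-point absolute margin in Section 4.1.

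**2. What the listed covariates can separate.** Take two patients with the same cancer (and the same stage, if the survival source uses stage).

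| | Treated a few months before PET, no visible disease | Diagnosed eight years before PET, disease-free |
|---|---|---|
| `Fiveyr_atPET` | same value | same value |
| Cancer indicator | 1 | 1 |
| 20 PET flags | all 0 | all 0 |
| Years since diagnosis | not recorded | not recorded |

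If the recent case has visible disease, the flags differ and the pair is separated. The gap is therefore confined to flag-negative patients. Disease-status strata built from the same flags do not close it. Section 4.1 counts progression as part of disease status, but Section 7 defines no progression or remission variable. The sentence in Section 8.4.5 could be read as making disease status an input to the survival probability, but Section 7 does not define the score that way.

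**3. How far the score can be from prognosis at PET.** Illustrative mixture-cure model; the 5-year survival S5 and cured share c are assumptions:

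- S(t) = c + (1 − c)·exp(−λt), with λ = −ln[(S5 − c)/(1 − c)]/5
- 5-year survival from a PET done x years after diagnosis = S(x+5)/S(x)
- 7-year mortality from that PET = 1 − S(x+7)/S(x)

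Worked case, S5 = 0.15 and c = 0.10: λ = −ln(0.05/0.90)/5 = 0.578. Then S(7) = 0.1157, S(10) = 0.1028 and S(12) = 0.10087. Five-year survival from a PET at x = 5 is 0.1028/0.15 = 0.685, while the score stays at 0.15. Seven-year mortality is 1 − 0.1157 = 0.884 at x = 0 and 1 − 0.10087/0.15 = 0.328 at x = 5, a gap of 0.557 before rounding.

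| S5 (score) | c | x = 0 | x = 2 | x = 5 | 7-year mortality gap, x = 0 vs 5 |
|---|---|---|---|---|---|
| 0.15 | 0 | 0.150 | 0.150 | 0.150 | 0 |
| 0.15 | 0.03 | 0.150 | 0.182 | 0.299 | 0.161 |
| 0.15 | 0.10 | 0.150 | 0.302 | 0.685 | 0.557 |
| 0.30 | 0.10 | 0.300 | 0.353 | 0.481 | 0.205 |
| 0.30 | 0.20 | 0.300 | 0.444 | 0.708 | 0.441 |
| 0.65 | 0.50 | 0.650 | 0.733 | 0.838 | 0.219 |
| 0.90 | 0.50 | 0.900 | 0.904 | 0.911 | 0.015 |
| 0.90 | 0.80 | 0.900 | 0.920 | 0.944 | 0.055 |

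The columns for x give 5-year survival from the PET. The error is zero under a constant hazard, small at 90% survival, and large for poor-prognosis cancers with a cured share.

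**4. What that could do to the risk difference.** Bias ≈ (between-arm difference in the share of long-term survivors that remains after weighting) × (7-year mortality gap). The documents give neither factor.

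- 10-point imbalance, 90%-survival cancer: 0.10 × 1.5 to 5.5 points = 0.15 to 0.55 points.
- 10-point imbalance, gap of 20 to 40 points: 0.10 × 20 to 40 = 2 to 4 points.
- Imbalance of 5 to 20 points, gap of 10 to 40 points: from 0.05 × 10 = 0.5 points to 0.20 × 40 = 8 points.

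The imbalance that matters is the one left after weighting on the flags, age, comorbidity and the other covariates. To the extent that these track recency, they shrink it, by an amount that cannot be computed from the documents.

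**5. Direction.** If long-term survivors more often have the ultrasound, the no-ultrasound arm looks worse and the bias works against non-inferiority. If they have it less often, the bias favours non-inferiority. The documents support neither pattern.

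**The case against.** The strongest reply is that the plan already measures current disease. Twenty flags from the index PET are in the adjustment set, and disease status at PET is a stratifier alongside the survival score. All flags at zero is itself informative. A newly diagnosed patient and a long-term survivor will usually differ on the flags, so a reader who infers that the weights and strata are misclassified outright goes too far. This stands, and it limits the problem to flag-negative patients.

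Second, the large errors come from chosen cure fractions and poor-prognosis cancers. Good-prognosis cancers are where 5-year survivors accumulate; in the worked case only 15% reach five years. This also stands. A reader might take the 2-to-4-point illustration as the expected bias, or assume that the ultrasound arm gains from it. The documents give no distribution of time since diagnosis and no data on who receives ultrasound, so they support neither inference.

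Third, it is an inference that the score depends on cancer type alone, because the survival source and any use of stage are unstated. That is correct, but stage at diagnosis would not supply recency either.

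Fourth, years since first diagnosis would by itself make a late recurrence look like long survivorship. The fix has to allow for this.

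None of these replies supplies a covariate that distinguishes recent from remote cancer among flag-negative patients.

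**Conclusion.** The point holds as a gap in one prognostic covariate. Followed as written, Section 7 gives recent and remote diagnoses of the same cancer one score and records recency nowhere else. Flag-negative recently treated patients and flag-negative long-term survivors stay pooled in the severity strata, and the weights do not separate them by recency.

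The consequence is possible residual confounding of undetermined sign. Its size runs from zero (constant hazard), through a few tenths of a point (good-prognosis cancers), to several points (poor-prognosis cancers with a cured share and a sizeable remaining imbalance). These sizes rest on the assumed cure model, which ignores other causes of death, and on assumed imbalances. The documents do not show that the primary result is biased by any particular amount. The change is still worth making before analysis, because it is cheap and the covariate is central to the adjustment.

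**What to change.** - **Derive recency.** For each pre-PET cancer, compute years from its first recorded code to the PET, using the dates of the ICD codes already queried.
- **Adherence model (Section 1.2, step 3).** Add years since the diagnosis that sets `Fiveyr_atPET` and years since the most recent cancer diagnosis. Interact them with `Fiveyr_atPET` and with an indicator of any active disease on the PET flags, so that a late recurrence is not scored as long survivorship.
- **Strata (Sections 4.1 and 8.4.5).** Split or report the survival-based strata by recent versus remote diagnosis, with the cut-point fixed in advance. Survival conditional on years already survived is an option if the survival source supports it.
- **Definitions.** Name the survival source, say whether stage is used and how patients with no prior cancer are coded, define the progression variable, and state whether disease status is a second stratifier or an input to the survival value.

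The cost is two derived variables, a few model terms and some text. Conditional-survival strata would need an external table that the plan does not name, so they are optional. One small downside is that the first-code date makes an old cancer look new in patients who joined the system late; a sensitivity analysis limited to recent diagnoses would help to show how much recency matters.
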